### 11.8.2. Additional Secondary Endpoints

### **Pharmacokinetic Analyses**

PK analysis will be conducted for magrolimab on the PK analysis set (PAS). Based on the distinct MOAs of magrolimab and azacitidine, overlapping drug PK interactions are not expected. Thus, samples for PK analysis for azacitidine will be banked and will be conducted based on CTSC recommendation.

The PAS consists of all treated patients who have at least 1 blood sample that provides evaluable PK data. The PAS will be used for summaries of PK concentration data, and PK parameters. Individual patients may be removed from the estimation of particular PK parameters based on the number of available blood samples for them. These patients will be identified at the time of analysis.

Depending on availability of data, the following PK parameters after the first and after multiple doses may be calculated using noncompartmental analysis:

- AUCtau (the area under concentration curve during a dosing interval)
- Cmax (maximum observed serum concentration)
- CL (clearance)

Additional PK parameters may also be calculated, if relevant.

Biofluid concentrations will be expressed in mass per volume units. All concentrations below the limit of quantification or missing data will be reported as such in the concentration data listings. Concentrations below the limit of quantification will be treated as zero in summary statistics.

Descriptive statistics of all PK parameters will include arithmetic and geometric mean, median, SD, CV, geometric coefficient of variation (CV), minimum and maximum. Zero concentrations will not be included in the geometric mean calculation. Since time to maximum concentration ( $T_{max}$ ) is generally evaluated by a nonparametric method, median values and ranges will be provided for this parameter.

Summary statistics will be presented for magrolimab serum concentrations at each scheduled time point. Descriptive graphical plots of individual serum concentration-versus-time profiles and mean concentration-versus-time profiles will be generated.

Missing concentration values will be reported as is in data listings. Concentration values below lower limit of quantitation will be handled as zero in summary statistics, and reported as is in data listings. Any missing PK parameter data will not be imputed.

All data from this study may be combined with PK data from other company-sponsored clinical studies and analyzed using a population PK model. Such an analysis would be reported separately.

### **Immunogenicity Analyses**

The rate and magnitude of anti-magrolimab antibody incidence and prevalence will be evaluated for individual patients, for all patients in each of the study cohorts, and for the pooled patient population.

Immunogenicity analysis may also be performed for azacitidine. However, it is not expected that magrolimab will impact the immunogenicity of azacitidine and vice versa.

### Immunogenicity: Exposure and/or Adverse Event Relationship

The concentration-versus-adverse event/immunogenicity relationship will be explored graphically, tabulated, and, if appropriate, evaluated by a mixed effects model in order to characterize a relationship between the changes from screening immunogenicity presence and serum concentration of magrolimab.

In addition, the potential correlation between immunogenicity and other endpoints (major safety, efficacy, and biomarker parameters) may be evaluated. This will be done in 2 steps. First, a descriptive analysis will be performed graphically between immunogenicity change from screening values and major safety, efficacy, and biomarker parameters. Second, for any potential correlation identified, further investigation will be performed using a mechanism-based modeling approach, as appropriate.

# 11.8.3. Safety Analyses

The statistical analysis of safety data will be conducted in patients who received at least 1 dose of magrolimab. Safety variables may include, but are not limited to: DLTs, treatment-emergent adverse events (TEAEs; AEs worsening or occurring during or after a patient's first exposure to study drug), vital signs, physical examinations, laboratory tests, RO (US only), and anti-drug antibody assessments.

Data will be presented by cohort (R/R or TN/U) and by treatment, when appropriate, as well as all cohorts combined. Some safety data may be summarized across multiple study cohorts or over all cohorts. Data may be graphed, summarized, or listed, depending on the amount of data to be reported. Where relevant, safety data will also be presented by the study day/study day interval corresponding to dose administrations within each dose cohort.

#### 11.8.3.1. Adverse Events

Adverse events will be coded using Medical Dictionary for Regulatory Activities (MedDRA) version 17.1 or later and the NCI CTCAE v 4.03 (Appendix A) will be used to grade severity of AEs and laboratory toxicities. Patient incidence of TEAEs and treatment-related TEAEs will be summarized by system organ class and preferred term. TEAEs will also be summarized using Investigator assessment of the relationship to study drug (related or not related). SAEs, including deaths, will be summarized and/or listed for each cohort and for all cohorts combined. TEAEs resulting in withdrawal from study drug or further study participation will be tabulated and/or listed. DLTs will also be listed.

Adverse events that occurred during screening, but before exposure to study drug will be reported in the AE line listings and appropriately identified as non-TEAEs.

Adverse events and SAEs occurring during screening will be reported separately for patients who were screened, but not entered in the study, with line listings and/or summary tables, along with relevant demographic data collected.

## 11.8.3.2. Analysis of Other Safety Endpoints

For select laboratory parameters, changes of laboratory values over time, grade shifts in laboratory value from baseline to worst on-study value and Grade 3 or higher laboratory toxicities will be summarized. The number and incidence of patients developing RO (US only) and ADAs at any time will be summarized. Vital signs and physical examination will be summarized at select time points. Details will be provided in the SAP.

## 11.9. Handling of Missing Data

Details regarding the handling of missing data will be described in the SAP.

## 11.10. Interim Safety Review

An interim safety review will be performed for patients in the R/R Cohort, TN/U AML Expansion Cohort, and the RBC Transfusion-dependent Low-risk MDS Cohort. After the first 10 patients are enrolled in each cohort, if >33% of patients experience an AE that qualifies as a DLT and results in permanent study drug discontinuation, withdrawal, or death, then that cohort will be stopped for unacceptable toxicity. If a study drug-related death occurs on study, a safety review will be conducted by the CTSC to determine whether enrollment should be interrupted. The trial may also be stopped at any time if the CTSC deems that there is an unacceptable safety risk to patients with the study treatment.

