
patients beyond the 20 patients for further safety, efficacy, and/or dosing data. Per CTSC decision in July 2020 and captured in Amendment 7, an additional 30 TP53 mutant AML patients were added to the TN/U Expansion Cohort (n = 62).

The RBC Transfusion-dependent Low-risk MDS cohort will consist of approximately 20 patients and be based on a Q4W magrolimab dosing schedule administered starting Cycle 2. Given that a higher dose of magrolimab (60 mg/kg) will be tested in this cohort, the first 6 patients will be treated in a safety run-in cohort. These 6 patients will be treated with magrolimab monotherapy for the first 2 cycles, followed by a response assessment. Patients who do not respond to magrolimab monotherapy by this time may have azacitidine added to their treatment regimen. Based on the initial safety and efficacy data for these 6 patients, the CTSC will determine whether the remaining 14 patients will be treated as magrolimab monotherapy or in combination with azacitidine, as well as the dose of magrolimab. After a safety evaluation of these 6 patients by the CTSC, the remaining 14 patients can be simultaneously enrolled. Based on emerging data, the CTSC may decide to enroll additional patients for further safety, efficacy, or dosing information. These additional patients may be treated with either magrolimab monotherapy or magrolimab in combination with azacitidine. Patients may have their magrolimab dose interval changed (i.e., to more frequent [Q2W] or less frequent [> Q4W]) at any time on therapy based on CTSC recommendations or Sponsor requirement.

The Rollover Cohort will be open to all patients (maximum of 8) on the existing Phase 1 AML trial (study SCI-CD47-002) who are deriving ongoing clinical benefit from magrolimab therapy. Patients in the Rollover Cohort may receive the same dose level and schedule (i.e., twice weekly) of magrolimab monotherapy as previously received on the Phase 1 AML study (SCI-CD47-002), or may transition to once-weekly dosing in this study at the discretion of the Investigator and with Sponsor approval. At the discretion of the CTSC for this study, Rollover patients who are receiving lower doses may be escalated to a higher dose deemed to be safe by the CTSC for this study.

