# 3.2. Study Design - R/R Cohort

The R/R Cohort will be evaluated in 3 stages. As of Amendment 3, in the first stage, 10 patients (the R/R Safety Cohort) have been treated in a safety run-in to evaluate the safety profile of magrolimab monotherapy in this R/R population. Based on aggregate clinical, safety, PK, and pharmacodynamic data in the R/R Safety Cohort, the CTSC will determine whether enrollment may begin in an Expansion stage of the initial R/R Cohort, in which a total of up to 36 additional patients in the R/R Expansion Cohort will be treated to evaluate the clinical activity of magrolimab in combination with azacitidine. In the R/R Expansion Cohort, magrolimab will be administered 1 mg/kg twice weekly for Cycle 1 Week 1 (Day 1 and Day 4); 15 mg/kg on Cycle 1 Day 8, 30 mg/kg on Cycle 1 Day 11 and Day 15, 30 mg/kg weekly on Cycle 1 Day 22 through end of Cycle 2, and 30 mg/kg Q2W starting Cycle 3 and thereafter, as shown in Table 3-1, based on clinical, PK, and pharmacodynamic data and for evaluation of a more convenient dosing regimen. If a patient has only received Day 1 treatment for a cycle, the patient may transfer to the Q2W dosing regimen with that cycle, for the balance of the cycle and beyond, even if they were previously receiving magrolimab QW at Cycle 3 and beyond.

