# 3.4.1. RBC Transfusion-dependent Low-risk MDS Cohort Definition of Dose-limiting Toxicity

DLT definitions for the RBC Transfusion-dependent Low-risk MDS Cohort are similar to those for the TN/U Safety Evaluation Cohort and are defined in Section 3.3.5 with the exception that the DLT period is through the first 6 weeks (Cycle 2 Day 15). If the DLT rate is ≥ 33% in at least 6 patients enrolled, then the 60 mg/kg magrolimab dose would be considered to have exceeded the MTD. In this case, the CTSC may decide to proceed with expansion at a magrolimab dose regimen of 30 mg/kg QW for Cycle 2 followed by Q2W from Cycle 3 onward or explore a dose de-escalation to a lower magrolimab dosing regimen. The CTSC may decide to enroll additional patients in the safety run-in to further evaluate safety of the magrolimab 60 mg/kg dosing regimen or a lower dosing regimen. Patients may have their magrolimab dose interval changed (i.e., to more frequent [Q2W] or less frequent [> Q4W]) at any time on therapy based on CTSC recommendations or Sponsor requirement.

An efficacy assessment for the first 6 patients will be assessed at Cycle 3 Day 1. For patients who do not respond to magrolimab monotherapy, azacitidine can be subsequently added for continuation of therapy according to the dose schedule in Table 7-3. After the 6 patients have completed their post-Cycle 2 efficacy assessment, the CTSC will determine based on safety and efficacy data whether further expansion to 14 additional patients will occur with magrolimab monotherapy or magrolimab in combination with azacitidine. Expansion of these 14 patients can be simultaneously enrolled. Based on emerging safety, PK/PD, and/or efficacy data, the CTSC may expand this cohort to additional patients beyond the 20 total with either magrolimab monotherapy or in combination with azacitidine.

Table 3-3. Dose Level and Schedule for RBC Transfusion-dependent Low-risk MDS Cohort

Cohort/Dose	Dose Schedule (Day per 28-day Cycle			-day Cycle)
Level	Drug/Dose/Route	Cycle 1	Cycle 2	Cycle 3+
Safety Run-in	Magrolimab - 1 mg/kg IV	Day 1	<del></del>	_
(Magrolimab 60 mg/kg)	Magrolimab - 30 mg/kg IV	Day 8, 15, 22	<del></del>	_
·	Magrolimab - 60 mg/kg IV	_	Day 1	Day 1
	Azacitidine - 75 mg/m² SC or IVª	_	<del>_</del>	Days 1-5
Expansion	Magrolimab - 1 mg/kg IV	Day 1		_
	Magrolimab - 30 mg/kg IV	Day 8, 15, 22	<del></del>	_
	Magrolimab - 60 mg/kg IV d	_	Day 1	Day 1

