- h. Time point details for correlative studies are provided in Table 7-6.
- i. Time point details for PK studies are provided in Table 7-10.
- j. RO blood samples (US only) collected on Day 1 of every other cycle during Cycles 3 to 7, then every 4 cycles through Cycle 19, and then starting Cycle 23 and onwards every 6 cycles (same day as bone marrow RO samples). Beginning at Cycle 3 Day 1, pretreatment PK and ADA samples to be collected every other cycle through Cycle 7 and then every third cycle to Cycle 13.

- k. Samples to be collected before administration of either study drug (magrolimab or azacitidine), within 72 hours for initial dose and within 24 hours for subsequent doses.
- I. Time point details for RO studies are provided in Table 7-13.
- m. At each bone marrow time point, both trephine (biopsy) and aspirate samples are to be collected for response assessment as well as CD47 receptor occupancy (US only), MRD assessment, correlative studies, and biobanking. Conventional cytogenetics to be tested per institutional standards.
- n. MRD monitoring to be performed on bone marrow aspirate samples obtained at the bone marrow biopsy time points.
- o. The first bone marrow assessment will occur at Cycle 3 Day 1 (± 3 days), approximately 8 weeks after the start of study treatment. Subsequent bone marrow assessments while on study treatment will occur every other cycle through Cycle 7 (i.e., Cycle 5 Day 1 and Cycle 7 Day 1). After Cycle 7 Day 1, bone marrow biopsies will be collected every 4 cycles through Cycle 19 (i.e., Cycle 11 Day 1, Cycle 15 Day 1, and Cycle 19 Day 1) and then starting Cycle 23 and onwards, bone marrow biopsies will be collected every 6 cycles (Cycle 23 Day 1, Cycle 29 Day 1, etc.).
- p. Response assessments may be adjusted by ± 4 weeks to coordinate with treatment cycle timing. After Cycle 3, the window is ± 14 days.
- q. Vital signs prior to infusion/injection and within 30 minutes after the end of each infusion/injection, before and after administration of each study drug (magrolimab or azacitidine). Weight at screening and Day 1 of each cycle. Details are provided in Section 7.3.5.
- r. Full PE at screening, symptom-directed PE thereafter. For Cycles 4 and beyond, PEs may be done only on Day 1 of each cycle, at the discretion of the Investigator.
- s. DLT will be assessed throughout the first 6 weeks of study treatment for the safety run-in part only.

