## 11.4. Sample Size Determination

The number of patients planned for inclusion in this trial is up to a total of approximately 287 patients evaluable for efficacy, as follows:

- R/R Safety Cohort: 10 patients
- R/R Expansion Cohort: Up to 36 patients
- R/R MDS Magrolimab Monotherapy Cohort: 23 patients
- TN/U Dose Evaluation Cohort: Up to 18 patients
- TN/U Expansion Cohort: Up to 172 patients, including
  - Original 30 TN/U Expansion (enrolled 18 AML and 16 MDS patients, including 4 replacement patients)
  - At least 92 MDS patients (including the original 16 MDS patients enrolled in the original TN/U Expansion), of whom at least 56 patients will be on Q2W dosing. The overall MDS expansion to 92 patients will be considered the MDS Registrational Cohort.
  - Up to 62 TP53 mutant AML patients (i.e., 12 original TP53 mutation AML patients, plus 20 additional TP53 mutant AML patients added per CTSC decision in September 2019, plus 30 additional TP53 mutant AML patients per CTSC decision July 2020)
- RBC Transfusion-dependent Low-risk MDS Cohort: Up to 20 patients
- Rollover Cohort: Up to 8 patients

For the R/R Safety Cohort, 10 patients have been enrolled as of the approval of Amendment 5 for evaluation of safety of magrolimab monotherapy.

For the R/R Safety Cohort and Expansion Cohort, approximately 46 patients may be enrolled, including 10 patients treated in the safety run-in cohort and 36 patients treated in the expansion cohort. For the R/R Safety Cohort, 10 patients were enrolled and this cohort was closed to further enrollment as of Amendment 3. Based on safety and efficacy data, the CTSC may decide to expand the R/R Expansion Cohort to include additional patients. An ORR of 17% has been reported in patients with R/R AML who have been treated with azacitidine (Itzykson 2015). For an estimated response rate of 33% or higher, 36 patients would provide a 95% confidence interval, with the lower bound to exclude 18.6%, the azacitidine monotherapy efficacy rate.

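### Section 11.10 counts its toxicity stop on the first 10 patients of each cohort, so read literally it sees none of the R/R combination patients and at most 4 of 10 in low-risk MDS

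*Protocol*

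**What the plan says.** Section 11.10 lists the groups covered: "An interim safety review will be performed for patients in the R/R Cohort, TN/U AML Expansion Cohort, and the RBC Transfusion-dependent Low-risk MDS Cohort". The trigger follows: "After the first 10 patients are enrolled in each cohort, if >33% of patients experience an AE that qualifies as a DLT" and that event results in permanent discontinuation of study drug, withdrawal or death, the cohort stops. The same section adds a Clinical Trial Steering Committee (CTSC) review after any drug-related death and a discretionary stop at any time, neither with a number attached.

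On the R/R Cohort, Section 3.2 says "The R/R Cohort will be evaluated in 3 stages", and that in the first of these "10 patients (the R/R Safety Cohort) have been treated in a safety run-in to evaluate the safety profile of magrolimab monotherapy". The azacitidine combination follows in the Expansion stage. Section 11.4 gives the sizes: "including 10 patients treated in the safety run-in cohort and 36 patients treated in the expansion cohort".

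On the low-risk MDS cohort, Section 3.1 says of the run-in: "These 6 patients will be treated with magrolimab monotherapy for the first 2 cycles, followed by a response assessment". Table 3-3 allows azacitidine for non-responders from Cycle 3. Section 3.4.1 ends the DLT period at Cycle 2 Day 15. The CTSC then decides whether the next 14 patients receive monotherapy or the combination, and "Expansion of these 14 patients can be simultaneously enrolled".

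On DLTs, Section 3.3.5 restricts them to the TN/U Dose Evaluation Cohort and the low-risk MDS cohort. Table 7-3 footnote s is narrower still: "DLT will be assessed throughout the first 6 weeks of study treatment for the safety run-in part only".

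**The concern.** A stopping rule should be read on the patients who receive the regimen being expanded. Here the count is tied to enrollment order within a cohort, and in two of the three named cohorts the earliest patients were deliberately treated without azacitidine. The look can then be passed, or largely filled, by monotherapy patients, and passing it says little about the combination.

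A second problem is the event itself. Section 11.10 counts DLT-qualifying events in the R/R and TN/U AML Expansion cohorts, where Section 3.3.5 says DLTs do not apply. It also counts them in low-risk expansion patients, for whom footnote s schedules no DLT assessment. Two people applying the rule to the same data could count different events.

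**Working it through.** The protocol states no operating characteristics for this rule, so there is no figure to reproduce. The cohort counts reconcile: 10 + 36 = 46 (R/R Safety and Expansion) and 6 + 14 = 20 (low-risk).

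**Threshold.** The smallest x with x/n above 0.33: n = 10 gives 4 (3/10 = 30%, 4/10 = 40%); n = 20 gives 7; n = 46 gives 16.

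**Assumptions.** True event rates are not in the protocol. I take 40% and 50% on the combination (pc) and 0 to 20% on monotherapy (pm), with patients independent.

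**R/R, literal reading.** The first 10 are the 10 monotherapy patients, so P(stop) = P(Bin(10, pm) ≥ 4) = 0, 0.001, 0.013 and 0.121 at pm = 0, 5, 10 and 20%. pc does not enter the formula.

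**Low-risk, literal reading, expansion on the combination.** The first 10 are 6 monotherapy and 4 combination patients. P(stop) = Σ over i of P(Bin(6, pm) = i) × P(Bin(4, pc) ≥ 4 − i).

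- pm = 0: all 4 of 4 are needed, so 0.4⁴ = 0.026 and 0.5⁴ = 0.063.
- pm = 5%: 0.078 at pc = 40% and 0.142 at 50%.
- pc = 50% with pm = 10% and 20%: 0.227 and 0.402.
- Comparator, ten combination patients: P(Bin(10, pc) ≥ 4) = 0.618 at 40% and 0.828 at 50%.

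Section 3.4 says expansion may proceed if there is no more than 1 DLT in the 6 run-in patients. With exactly one event carried over, 3 of the 4 combination patients are needed: 4(0.4³)(0.6) + 0.4⁴ = 0.179 at 40%, and 4(0.5³)(0.5) + 0.5⁴ = 0.313 at 50%.

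**Cumulative reading** (checking continues after patient 10, everyone in the denominator, no monotherapy events; each probability is for a single look):

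| Cohort | Combination patients so far | Events needed | P at pc = 50% |
|---|---|---|---|
| R/R | 10 | 7 of 10 | 0.17 |
| R/R | 36 | 16 of 36 (44%) | 0.80 |
| Low-risk | 4 | 4 of 4 | 0.06 |
| Low-risk | 14 | 7 of 14 (50%) | 0.61 |

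For low-risk at 14 combination patients the figure at pc = 40% is 0.31. The trigger exists on this reading, but monotherapy patients push the combination rate needed to fire it above 33%.

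**DLT passages side by side.** R/R and TN/U AML Expansion: counted in 11.10, excluded in 3.3.5. Low-risk expansion: counted in 11.10, included in 3.3.5, outside the scheduled assessment in footnote s. Azacitidine added to a run-in patient starts in Cycle 3, after the DLT period has ended at Cycle 2 Day 15.

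**The case against.** Several points on the other side carry weight.

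- **Cohort unit.** Section 11.4 and Table 3-1 list R/R Safety and R/R Expansion as separate cohorts. If that is the unit, the first 10 Expansion patients are all on the combination and the R/R problem disappears. But Section 11.10 names the R/R Cohort whole while specifying Expansion for TN/U AML, and Section 3.2 treats R/R as one staged cohort. The text does not settle it.
- **Continuing check.** The rule can be read as starting at patient 10 rather than as a single look. It does not say so, and that reading dilutes the rule without curing it.
- **Other safeguards.** The death review and discretionary stop cover combination patients. The 30 mg/kg combination also went through the TN/U Dose Evaluation Cohort (8 patients enrolled), and 36 TN/U patients had received it by May 2019 with no maximum tolerated dose reached. This bears on R/R Expansion; it does not cover 60 mg/kg with azacitidine in low-risk MDS.
- **Closed cohorts.** Tables 7-1 and 7-3 mark both cohorts closed to enrollment. This limits the practical effect.

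Two stronger readings are tempting. A reader might infer that the combination has no working trigger in either cohort. For low-risk MDS that is not so: the trigger can fire, and dilution arises only if the CTSC chose the combination. A reader might also infer from footnote s that the relevant events go unrecorded in expansion patients. Sections 7.3.9 and 9.2.1 require all adverse events to be collected from first dose to at least 30 days after last dose, subject in Section 9.2.1 to the start of another anti-cancer therapy. What is unclear is which of them count as DLTs.

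**Conclusion.** The point stands in limited form. On the literal reading, the Section 11.10 look contains 0 of 10 combination patients in R/R and at most 4 of 10 in low-risk MDS. In the latter the chance of stopping is 0.03 to 0.06 at combination rates of 40 to 50% with no monotherapy events. It rises to 0.40 at 50% combination and 20% monotherapy, against 0.62 to 0.83 for ten combination patients. The rates are assumptions; the composition of the first 10 is not, apart from the CTSC's choice for the low-risk expansion. On a cumulative reading the rule is weakened, not absent.

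The conflict over which patients' events are DLTs holds whatever rates are assumed. With both cohorts closed, what is at stake is the review of ongoing patients, any further expansion the CTSC opens, and the conclusion drawn from the rule: not having stopped at 10 is little or no evidence that the combination is tolerable.

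**What to change.** Reword Section 11.10, keeping its threshold, so that monotherapy and combination patients within a cohort are counted separately. Say whether R/R Safety and R/R Expansion are one cohort for this purpose, and whether the check is made once or continues. Reconcile Section 11.10 with Section 3.3.5 and Table 7-3 footnote s on which patients' events count as DLTs. How that is resolved, including any assessment window, is for the sponsor and the CTSC. In the report, state which regimen the patients in each look had received.

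The cost is wording: the adverse event data are already collected and the same committee reviews them. The downside is a slightly higher chance of a precautionary pause, since counting by regimen makes the rule easier to trigger on the combination.
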